**Sponsor or funding source:**

Departmental Funding

**Summary/Purpose/Rationale**

Regional anesthesia techniques are common modalities used to provide analgesia following both upper and lower extremity surgeries. Many different combinations of adjuvants added to local anesthetics for peripheral nerve blocks (PNB's) have been attempted to prolong the duration of analgesia following surgery. These adjuvants include clonidine, buprenorphine, tramadol, midazolam, and neostigmine [1]. In some preliminary studies, dexamethasone appears to prolong the duration of analgesia in both the perineural route and intravenous route [2, 3]. However, many of these studies were based on subjective primary end points, such as quality of recovery surveys or time to first opioid analgesic request [3,4]. Interestingly, a study out of Toronto has more completely shown what was already seen in preliminary studies, that both systemic and perineural steroids are also effective in prolonging the duration of peripheral nerve blocks [5, 6].

Dexamethasone, a glucocorticoid with minimal mineralocorticoid effect, has been shown to improve the overall quality of surgery in certain surgical populations as well as decrease the amount of opioid consumed when given intravenously [7]. Though there has been some concern regarding the potential neurotoxicity of dexamethasone, there have been multiple studies that purport to show no neurotoxic findings with single injection dexamethasone alone or in combination with local anesthetics as single injection doses [8, 9]. However, there have been limited human studies giving safety data [2]. Given this concern, it is paramount to determine if an effective lengthening of the peripheral nerve block can be accomplished with a lesser dose [10]. Many studies have used 4 mg and 8mg of dexamethasone perineurally, but none to our knowledge have compared a lower dose to see if it is equally effective while limiting potential neurotoxicity concerns [2]. The saphenous nerve would be an ideal nerve to study given that it is a sensory nerve with no motor function.

**Objectives**

The purpose of this randomized, double-blinded, placebo-controlled trial is to examine if dexamethasone given perineurally as an adjuvant to the nerve block will prolong the time to recovery from sensory nerve block. We hypothesize that dexamethasone will provide analgesic times greater than that seen in the control arm without dexamethasone, and that similar results will be obtained by the 1 mg arm when compared to the 4 mg arm. The primary outcome will be

time to resolution of the nerve block as assessed by pinprick over the saphenous nerve distribution. Secondary outcomes will include pain scores, amount of post-operative opioids, and the incidence of nausea and vomiting will be recorded over the course of 24-48hrs. This will be done by asking the patient about nausea and emesis following recovery. The answers will be recorded on the data sheet as yes or no. Subjects will also be followed to evaluate for potential neurologic complications such as persistent paresthesias in the distribution of the saphenous nerve.

### **Methods/Measurements:**

#### **Design:**

This study will be a randomized, double-blind, placebo-controlled trial that will take place after Institutional Review Board approval. Written informed consent will be obtained from all the study participants. We have already obtained an Investigational New Drug (IND) exemption from the Food and Drug Administration (IND 125810) for this study given the following protocol

### **Selection Criteria:**

Inclusion: Adults, between 18 and 90 years of age, undergoing elective robotic medial and/or patellofemoral MAKO partial knee arthroplasty and who have agreed to a regional anesthesia technique will be recruited to participate.

Exclusion: Subjects with contraindications to regional anesthesia, such as a history of allergy to amide local anesthetics, presence of a progressive neurological deficit, a pre-existing coagulopathy, infection, or the following conditions: insulin and non-insulin dependent diabetes mellitus, systemic use of corticosteroids within 30 days of surgery, chronic use of an opioid analgesic (>3 months or a combined total of more than 40 mg Oxycodone equivalents a day), or whom are pregnant will be excluded. Also, any patient with a prior history of an adverse event (for example: psychosis) or an allergy to dexamethasone will be excluded.

#### Setting:

All patients in the study will be undergoing non-urgent surgery at Wake Forest University Baptist Medical Center. The interventions will be performed in the regional anesthesia area of the surgery center.

### **Interventions and Interactions:**

Adults, between 18 and 90 years of age, undergoing elective robotic medial and/or patellofemoral MAKO partial knee arthroplasty will be recruited to participate. Eligible patients will be identified the day before surgery based on surgical postings. Upon arrival to the regional anesthesia area of surgical services at Wake Forest University Baptist Medical Center they will be formally consented if they are interested in participating in the study. Patients will be asked to provide baseline verbal pain scores both at rest and with movement on a scale of 0-10 (0 being no pain and 10 being the worst pain). Preoperative opioid use including drug, dosage and frequency will be recorded. Additionally, baseline patient characteristics will be recorded including height, weight, BMI, sex, age, surgeon and operative side.

Before PNB placement each patient will be randomized blindly to one of the three aforementioned arms. Blinding will occur by a secondary provider in the regional and acute pain management area by a second provider not associated with the study. This will obviously occur following randomization. All volumes will be identical. Once randomization and blinding occur, standard ASA monitors and oxygen will be applied. All saphenous nerve blocks will be performed by a resident or a fellow trainee supervised by an attending anesthesiologist. Sedation for the PNB will be provided in the usual manner at the discretion of the anesthesiologist providing the nerve block. Unless there is a contraindication, each patient will receive 1000 mg of PO acetaminophen, 150 mg of PO pregabalin, and 400 mg of celecoxib.

All subjects will receive an ultrasound-guided adductor canal nerve block and will be computer randomized to receive 20 ml of one of the following solutions: either 0.25% bupivacaine with epinephrine 1:400,000, 0.25% bupivacaine with epinephrine 1:400,000 with 4 mg of preservative free dexamethasone added to the solution, or 0.25% bupivacaine with epinephrine 1:400,000 with 1 mg of preservative free dexamethasone added to the solution. Both the subject and the investigator will be blinded to the arm of the study.

The products to be used are the following, and have been granted an FDA IND exemption (IND 125810)

- 1) Bupivacaine Hydrochloride. 30 ml single dose vial. 11 Digit NDC code: 00409-1159-02. Hospira, Inc. Lake Forest, IL.
- 2) Dexamethasone Sodium Phosphate Injection 10mg/ml. APP Pharmaceuticals LLC, Schaumburg, Ill. NDC Code: 63323-506-01, 63323-516-10
- 3) McKesson ID 2070274 Adrenalin Chl. Inj. 1mg/ml 1ML25 epinephrine NDC 2023015925.

For each nerve block, the epinephrine will be added to the bupivacaine and dexamethasone in a sterile fashion and used within 24 hours of the epinephrine being added. Otherwise, the solution will be discarded. All procedures will be performed under a sterile technique including the use of a chlorohexidine prep of the skin, sterile gloves, a sterile ultrasound probe cover with sterile ultrasound gel, and a cap and a mask. A 21-gauge 90 mm Arrow StimuQuick, stimulating needle (Teleflex, USA) will be directed under real-time ultrasound guidance into the adductor canal. The local anesthetic solutions will be injected incrementally in 5 mL aliquot to a total volume of 20 mL to surround the saphenous nerve.

Study subjects will receive either a spinal anesthetic with propofol sedation (25–100 µg/ kg/min) or a general anesthetic for their surgical procedure. Patients will undergo their surgery and be brought to the post-anesthesia recovery unit (PACU). The patient will remain in the PACU until resolution of the spinal from the non-operative side.

These participants will be observed overnight and will be evaluated every two hours with pin-prick (performed with a 25 gauge Whitacre needle in the cutaneous distribution of the saphenous nerve on the medial aspect of the blocked leg) to monitor for the duration of the sensory block until sensation is fully returned. This testing will be performed by research assistants. If the duration of their sensory block should last past admission, the patients will be educated during their hospitalization assessments on how to assess their own block every two hours at home using a safety pin. Research assistants will continue to call patient's every two to three hours

during this time until block resolution occurs to instruct the participants and answer any questions. During their stay, their pain management will be managed by the Acute Pain Service. They will also be asked about their pain using the visual analog scale, post operative nausea and vomiting rates, and opioid consumption will be followed. Comparisons will then be made between the three groups and the data will be analyzed.

### **Outcomes Measures:**

Subjects will be evaluated for the efficacy of a sensory blockade on the operative limb. Complete sensory analgesia will be defined as analgesia to pinprick in the distribution of the saphenous nerve. The primary outcome will be time to resolution of the nerve block as assessed by pinprick over the saphenous nerve distribution, secondary outcomes will include but not limited to pain scores, use of post-operative opioids, and the incidence of nausea and vomiting will be recorded over the course of 24-48hrs. Subjects will also be followed to evaluate for potential neurologic complications such as persistent paresthesias in the distribution of the saphenous nerve.

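### Opioid use and nausea/vomiting are promised over 24 to 48 hours, but the window has no fixed start or end and no scheduled contact assures data to 48 hours

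*Combined protocol and SAP*

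**What the plan says.** Two sections set the recording period. Outcomes Measures lists the secondary outcomes and says "use of post-operative opioids, and the incidence of nausea and vomiting will be recorded over the course of 24-48hrs". Objectives gives the same period and adds, for nausea and vomiting, "This will be done by asking the patient about nausea and emesis following recovery" and "The answers will be recorded on the data sheet as yes or no". Neither section gives a start, a required end or a clock time for the question.

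Interventions and Interactions is the only place that describes contacts with patients:

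- In hospital: "These participants will be observed overnight and will be evaluated every two hours with pin-prick". No discharge hour is given.
- After discharge: self-testing at home and telephone calls apply only on a condition, "If the duration of their sensory block should last past admission". The calls run "during this time until block resolution occurs to instruct the participants and answer any questions".
- Secondary outcomes: one sentence begins "During their stay, their pain management will be managed by the Acute Pain Service", and the next says "They will also be asked about their pain using the visual analog scale, post operative nausea and vomiting rates" and that opioid consumption will be followed. No time points are attached.

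The same section has baseline verbal pain scores taken at rest and with movement. No analysis that uses them is stated. For the secondary outcomes the plan says only that the three groups will be compared.

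**The concern.** Total opioid use and a yes/no answer on nausea both grow with the time a patient is observed. If one patient is observed for 20 hours and another for 30, their totals measure different things. A range of 24 to 48 hours does not say which total is the outcome, and the described contacts do not reach its upper end. At stake are the interpretability of two named secondary outcomes and the possible loss of the second day's data for many patients.

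A smaller point sits beside this. Baseline pain is measured in everyone, but no use of it is stated. Adjusting for it would sharpen the post-operative pain comparison at no cost in data, which is most useful against a control arm of only 15.

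**Working it through.** The plan gives no figure on this point to reproduce. The conclusion rests on the text; the calculations only size it.

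**1. Promise against schedule.**

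- To 24 hours: an overnight stay may reach this, but no hour is stated.
- From 24 to 48 hours, block resolved by discharge: no contact is scheduled.
- From 24 to 48 hours, still blocked at discharge: calls are made, but they end at resolution, and their stated purpose is to instruct and to answer questions. Collecting opioid or nausea data is not mentioned.

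**2. Would the calls reach 48 hours in any case?** Power / Sample Size cites a mean of 25 h, 95% CI 19.5-27.4, n = 25. The interval is asymmetric, so I take the SD as limb × √25 / q, with q = 2.064 (t, 24 df) or 1.96:

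- upper limb 27.4 − 25 = 2.4: SD 5.8 or 6.1 h
- half-width (27.4 − 19.5)/2 = 3.95: SD 9.6 or 10.1 h
- lower limb 25 − 19.5 = 5.5: SD 13.3 or 14.0 h

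Under a normal model the share resolved by 48 h is Φ((48 − 25)/SD):

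- SD 5.8: Φ(3.97), over 0.999
- SD 10.1: Φ(2.28) = 0.989
- SD 14.0: Φ(1.64) = 0.95

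So for about 95% to over 99% of dexamethasone patients the calls would have ended before 48 h. The cited study used 8 mg and a brachial plexus block and measured duration of analgesia, so this is illustration only.

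**3. Noise if the data are collected in the stay.** Assumptions, none from the documents: window length W uniform on 20-30 h; opioid use after 24 h at r = 0.25 to 1 times the day-1 rate; between-patient CV of the opioid rate (cv_x) 0.4 to 1.0; W independent of that rate. Effective exposure is the hours up to 24 plus r × the hours past 24.

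- CV of exposure (cv_w): 0.066 (r = 0.25), 0.082 (r = 0.5), 0.115 (r = 1). At r = 1, for example, the mean is 25, the SD is 10/√12 = 2.89, and 2.89/25 = 0.115.
- Variance inflation = [(1 + cv_w²)(1 + cv_x²) − 1]/cv_x² = 1 + cv_w²(1 + 1/cv_x²).
- Smallest (r = 0.25, cv_x = 1.0): 1 + 0.0044 × 2 = 1.009.
- Largest (r = 1, cv_x = 0.4): 1 + 0.0133 × 7.25 = 1.097.

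The variance of the opioid total therefore rises by about 1-10%.

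**4. The two ends of the stated range are different outcomes.** With a 24 h nausea risk p and a day-2 hazard r times that of day 1, the 48 h risk is 1 − (1 − p)^(1+r). For r from 0.25 to 1, a risk of 10% becomes 12-19%, 20% becomes 24-36% and 30% becomes 36-51%. This compares a full 24 h window with a full 48 h window. It shows why the end must be named, and it is not a measure of the noise in step 3.

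**5. Baseline pain as a covariate.** The variance of the comparison falls by ρ². At assumed ρ of 0.3, 0.5 and 0.7 the cut is 9%, 25% and 49%. Fifteen controls then give the precision of 15/(1 − ρ²) = 16.5, 20.0 and 29.4.

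**The case against.** The strongest reply is that the plan does state the recording period for all patients, and that time points normally sit on the Data Collection Form. The Appendix lists that form, but its content is not in the supplied text. The phrase about the stay opens the sentence on the Acute Pain Service, and the following sentence on pain, nausea and opioids carries no such limit. The plan also promises follow-up for persistent paresthesias, which implies contact after discharge. Discharge might well fall after 24 hours. These are secondary outcomes with no power claim.

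Much of this stands. The form may fix time points, the stay may cover 24 hours, and reading the data collection as in-hospital is likely rather than certain. But none of these places gives a time or mode of contact after discharge for opioid or nausea data, and the neurologic follow-up has no schedule either.

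A reader might infer something stronger: that because post-discharge calls depend on block status, patients on dexamethasone are observed longer and the comparison with control is biased. That would follow only if the calls also collected these outcomes. The text does not say they do, and it describes them as instructional. If collection ends with the stay, nothing in the documents ties the window to arm.

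**Conclusion.** The point holds for the secondary outcomes. As written, the plan promises recording over 24 to 48 hours, fixes neither end of the window, and schedules nothing that assures data to 48 hours for any patient. The observed window varies with discharge time. If the data are collected during the stay, the cost is modest noise, about 1-10% more variance in the opioid total, given assumed discharge at 20-30 hours and the assumed variability and day-2 rates above. Whatever is not collected after discharge is also lost.

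The documents do not support reading this as bias between arms, as a failure to collect 24 hour data, or as a threat to the primary outcome, which has its own follow-up to block resolution. The unseen form leaves some doubt about how much is already settled. The covariate point is a separate, free improvement whose size rests wholly on assumed correlations.

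**What to change.** - State one post-operative origin, such as end of surgery or arrival in the PACU. Analyse opioid use and nausea/vomiting over the same windows for every patient, 0-24 h and 24-48 h. An origin at block placement would not match an outcome defined as post-operative, because time to the end of surgery varies.
- Obtain data past discharge by one call at 48 h, made regardless of block status and using the same questions in all arms.
- If the Data Collection Form already holds fixed times, put them in the protocol and check that a scheduled contact serves each one.
- Compare post-operative pain at stated times, with the baseline pain score as a covariate.

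Cost: a change to the data form and at most 50 + 50 + 15 = 115 short calls, by assistants who are already to telephone patients at home. Post-discharge opioid use would rest on patient report. The covariate adjustment needs no new data.

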### **Analytical Plan:**

#### **Power / Sample Size:**

The primary sample size consideration is the comparison between the 1 mg and 4 mg of dexamethasone arms, where the goal is to demonstrate that the duration of PNB is clinically equivalent between the two arms. Note that this hypothesis, statistically, is reversed from what is usually tested in a superiority trial. We have assumed that clinically equivalent means that the average duration of PNB for 1 mg of dexamethasone is  $\pm$  4 hours from the average duration for 4 mg. In other words, the difference in mean duration for the two dexamethasone arms (D) falls on the interval (-4 hrs to 4 hrs). Statistically, a successful trial would then reject the null hypothesis  $H_0: D < -4$  hrs or  $D > 4$  hrs. The previously mentioned Toronto study [5] reported a mean duration of analgesia of 25 hours (95% CI: 19.5-27.4) for 25 patients randomized to 8 mg of perineural dexamethasone. While the test of clinical equivalence will be based on the boundary of  $\pm$  4 hours, in order to permit power calculations one has to make an assumption about the true difference in mean duration. The most liberal assumption is that there is absolutely no difference in mean duration between the arms (i.e.  $D=0$ ). To be more conservative, we have assumed that the true mean duration for 4 mg of dexamethasone is  $\pm$  1.5 hours from the true mean duration for 8 mg. This assumption implies that a study of 50 participants per group (allowing for 10% drop-out) will have  $>80\%$  power to declare the two doses as clinically equivalent. Note that this calculation assumes a type 1 error rate of  $0.05/3 = 0.1667$ , as the study has three planned comparisons (two dexamethasone doses versus each other, and then both versus the placebo control). We plan to recruit a reduced sample size for the placebo control arm, as the difference in duration of PNB when compared to both dexamethasone arms is expected to be large. Provided the average duration of PNB is at least 5 hours longer for either dexamethasone arm, we will have  $>90\%$  power recruiting only 15 subjects (allowing for 10% drop-out) to the placebo control arm. Note that the Toronto study [5] reported an average improvement of 11.8 hours when comparing 8 mg of perineural dexamethasone to their control arm.

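### The per-comparison alpha is misprinted (0.05/3 is 0.0167, not 0.1667) and no SD is given, so the stated power cannot be confirmed; as a minor second point, the success criterion does not mention placebo

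*Combined protocol and SAP*

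**What the plan says.** The Analytical Plan of the combined protocol and SAP consists of one paragraph, Power / Sample Size.

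- **Alpha.** The type 1 error rate is given as 0.05/3 = 0.1667, "as the study has three planned comparisons (two dexamethasone doses versus each other, and then both versus the placebo control". Sidedness is not stated.
- **Equivalence.** The margin is ±4 h on the difference D in mean block duration. With 50 per dexamethasone arm, allowing for 10% drop-out, power is put above 80%. The assumed true difference of ±1.5 h is worded for 4 mg against 8 mg.
- **Placebo.** With 15 placebo patients, also allowing for 10% drop-out, power is put above 90%: "Provided the average duration of PNB is at least 5 hours longer for either dexamethasone arm".
- **Variability.** No SD is stated. The only information on spread is the cited Toronto study, which "reported a mean duration of analgesia of 25 hours (95% CI: 19.5-27.4) for 25 patients" given 8 mg.
- **Success.** "Statistically, a successful trial would then reject the null hypothesis", namely that D lies outside ±4 h. No placebo result is mentioned there.

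Elsewhere, the Summary/Purpose/Rationale says that "it is paramount to determine if an effective lengthening of the peripheral nerve block can be accomplished with a lesser dose". The Objectives give the purpose as "to examine if dexamethasone given perineurally as an adjuvant to the nerve block will prolong the time to recovery from sensory nerve block" and add: "We hypothesize that dexamethasone will provide analgesic times greater than that seen in the control arm without dexamethasone". They hypothesize similar results for 1 mg and 4 mg alongside. Interventions and Interactions closes with "Comparisons will then be made between the three groups and the data will be analyzed".

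**The concern.** The printed alpha is ten times the value of its own fraction. With no SD, a reader cannot recover from the power claims which alpha was used. If the calculation used 0.1667, the trial is smaller than the intended 0.05/3 requires. If it used 0.0167, it needed an SD well below anything the cited interval suggests. Either way, the >80% and >90% that justify 50, 50 and 15 patients cannot be checked.

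The second matter is interpretive. The rationale asks whether a lower dose still lengthens the block. Equivalence of two active arms does not answer that alone, because two doses that both do nothing are also equivalent. The plan does not say how to read a trial in which equivalence is met but 1 mg is not shown to beat placebo, so that reading could be chosen after the data are seen.

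**Working it through.** **Inputs from the plan:** margin 4 h; 50/50/15 recruited; 10% drop-out; placebo gain 5 h; three comparisons; cited interval 19.5 to 27.4 around 25, n = 25.

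**Assumptions:** evaluable 45/45/13 (50 × 0.9 = 45; 15 × 0.9 = 13.5, rounded down); D = 1.5 h applied to 1 mg against 4 mg; normal durations with equal SDs; two-sided placebo tests; equivalence by two one-sided tests, each at the stated alpha.

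**1. Alpha.** 0.05/3 = 0.01667.

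**2. SDs readable from the interval** (SD = half-width × √25 / quantile; t on 24 df = 2.064). The interval is not symmetric about 25.

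- Upper half: 2.4 × 5 / 2.064 = 5.81 h
- Full width: 3.95 × 5 / 2.064 = 9.57 h, or 3.95 × 5 / 1.96 = 10.08 h
- Lower half: 5.5 × 5 / 2.064 = 13.32 h

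**3. Formulas.**

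- Equivalence power ≈ Φ((4−D)/se − z) + Φ((4+D)/se − z) − 1, with se = SD√(2/45) and z the 1−alpha quantile.
- Placebo power ≈ Φ(5/se − z), with se = SD√(1/45 + 1/13) and z the 1−alpha/2 quantile.

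Example for equivalence at SD 5.81 and alpha 0.0167: se = 1.225, z = 2.128, so Φ(−0.087) + Φ(2.362) − 1 ≈ 0.46. The exact t-based value is 0.444.

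**4. Reproducing the plan's figures** (t-based):

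| SD (h) | Equivalence, 0.0167 | Placebo, 0.0167 | Equivalence, 0.1667 | Placebo, 0.1667 |
|---|---|---|---|---|
| 3.94 | 80% | 94% | 98% | >99% |
| 4.21 | 74% | 90% | 97% | 99% |
| 5.81 | 44% | 61% | 86% | 91% |
| 9.57 | 0.7% | 22% | 57% | 60% |
| 10.08 | 0.2% | 20% | 53% | 57% |

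At 0.0167 the equivalence claim needs an SD of at most 3.94 h and the placebo claim at most 4.21 h. At 0.1667 the limits are 6.52 h and 5.91 h. The stated powers therefore fit both an SD just under 4 h with the right alpha and an SD of 5.8 h with the misprinted one.

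**5. Success criterion** (simulation under the same assumptions, at least 200,000 trials per scenario; gains over placebo listed for 1 mg, then 4 mg).

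- *Both doses inert:* equivalence at 0.0167 is met in 99% of trials at SD 4, 73% at SD 5.8, 0.9% at SD 9.57 and 0.2% at SD 10.08. Equivalence together with both placebo tests, all at 0.0167, is met in 0.2% at SD 4 and 5.8.
- *Equivalence met but at least one placebo test failed, alpha 0.0167:* at gains of 5 and 6.5 h, 4% (SD 4) and 14% (SD 5.8). At 3 and 4.5 h, 38% and 33%. At 10.3 and 11.8 h, about 0%. At SDs near 10 h it is below 1% throughout, because equivalence is then almost never declared.
- *Two-part rule (1 mg beats placebo and is equivalent to 4 mg), each part at 0.05:* at gains of 5 and 6.5 h it succeeds in 88% (SD 4), 53% (SD 5.8), 9% (SD 9.57) and 6% (SD 10.08). With inert doses it succeeds in 2.5% (SD 4) and 2.0% (SD 5.8).
- *Also requiring 4 mg to beat placebo:* this costs under 2 points when 1 mg is the shorter arm. When 1 mg is the longer (gains of 4.5 and 3 h), success falls from 84% to about 60% at SD 4 and from 40% to about 26% at SD 5.8.

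**The case against.** **On alpha and power.** The fraction 0.05/3 shows what was meant, so 0.1667 may be only a slipped decimal, and the sponsor may hold an SD near 4 h from another source. Both are possible, and then the stated powers stand. But the plan gives no such SD, and the one interval it cites does not yield it.

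The shortfall at SD 5.8 is not an artefact of strict assumptions taken singly. Equivalence power stays at or below about 50% with no drop-out and is 73% with D = 0. Placebo power is about 79% with no drop-out and a one-sided test. Only D = 0 and no drop-out together bring equivalence to about 81% (se = 5.81√(2/50) = 1.162; 2Φ(4/1.162 − 2.128) − 1), and the plan expressly adopts neither.

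A reader might infer that 0.1667 was really used, or that the interval's half-width of 3.95 h was mistaken for an SD. The documents support neither inference. They show only that the calculation cannot be identified.

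**On the success criterion.** The Objectives already pair superiority over control with similarity of the doses. Both placebo comparisons are planned, powered and included in the alpha split. The success sentence explains why the null is reversed and need not be a rule for the whole trial. All of this stands and makes the second point minor.

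A reader might infer that the plan would pass two inert doses 99% of the time. That figure ignores placebo tests that will be run and reported. A reader might also infer that both doses must beat placebo before 1 mg can be supported. The rationale asks only about the lesser dose, and the extra condition has the cost shown above. Nor is the flat three-way split an error: it is valid.

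**Conclusion.** The main point holds as an error in the text: 0.05/3 is 0.0167. At that alpha, the >80% and >90% hold together only for an SD of about 3.9 h or less. SDs read from the cited interval give at most about 44% and 61%, and at 9.6 to 10.1 h under 1% and about 20 to 22%. These sizes rest on an SD that the plan does not state, on D = 1.5 h carried over to 1 mg against 4 mg, and on 45/45/13 evaluable. They do not establish that the trial is underpowered, only that its stated power is unverified and may be too favourable.

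The missing link between equivalence and placebo is a minor clarification. It matters mainly if gains over placebo are modest, and hardly at all if they approach the cited 11.8 h.

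**What to change.** **Main.** In Power / Sample Size, correct 0.1667 to 0.0167. State the SD and its source. State the assumed true difference for 1 mg against 4 mg and the sidedness of each test. Confirm which alpha the calculation used, and restate both powers. This is desk work. The downside is that the restated power may be less favourable, which would raise the question of sample size.

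**Minor.** Add a sentence such as: the trial supports the 1 mg dose only if 1 mg is superior to placebo and equivalent to 4 mg within ±4 h; if equivalence is met but 1 mg is not shown superior to placebo, it does not. Because both parts must pass (an intersection-union test), each may be tested at 0.05 without a split: the placebo test two-sided and in the right direction, and equivalence by a 90% confidence interval within ±4 h. Restate power for this claim, which rests on about 13 evaluable placebo patients. Report 4 mg against placebo alongside, not as a condition for the 1 mg claim.

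If the three comparisons are also to be claimed individually, keep 0.05/3 (or Holm) for those claims, and say in advance which claim is primary. None of the wording changes needs extra patients.

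### Does labelling the ±1.5 h planning difference as 4 mg versus 8 mg undermine the sample size for the 1 mg versus 4 mg equivalence test?

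*Combined protocol and SAP*

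**What the plan says.** All the relevant text is in the Power / Sample Size section under Analytical Plan. It opens with the contrast: "The primary sample size consideration is the comparison between the 1 mg and 4 mg of dexamethasone arms". Success is defined for that contrast: "the difference in mean duration for the two dexamethasone arms (D) falls on the interval" from -4 to 4 hours. An external study is then cited, with a mean of 25 hours (95% CI 19.5 to 27.4) "for 25 patients randomized to 8 mg of perineural dexamethasone".

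The section next explains that a power calculation needs a value for the true difference, and starts with zero: "The most liberal assumption is that there is absolutely no difference in mean duration between the arms". As the more conservative alternative it says "we have assumed that the true mean duration for 4 mg of dexamethasone is" ± "1.5 hours from the true mean duration for 8 mg". It states that this assumption leads to 50 participants per group after a 10% drop-out allowance, with more than 80% "power to declare the two doses as clinically equivalent".

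The arms listed under Interventions and Interactions are placebo, 1 mg and 4 mg. The three planned comparisons are the two doses against each other and each against placebo.

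**The concern.** The planning difference is one of the most influential inputs to an equivalence sample size. Here it is attached to 4 mg versus 8 mg, which the trial does not compare. The only difference printed for 1 mg versus 4 mg is zero, and the plan declines to use it. On a literal reading, the 50 per group and the power above 80% rest on an assumption about a different pair of doses. Closeness of 4 mg to 8 mg would say nothing about closeness of 1 mg to 4 mg. If the true 1 mg versus 4 mg difference assumed were really something else, the stated power could be badly wrong.

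**Working it through.** **Reading the sentences together**

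1. The section says power needs an assumed true difference in mean duration, having already defined D as the difference between the two dexamethasone arms of this trial.
2. It offers D = 0 between the arms as the liberal choice.
3. It introduces 1.5 h as more conservative than that. An assumption about 4 mg versus 8 mg supplies no D, so it cannot be more or less conservative than D = 0. The comparison works only if 1.5 h is another value of the same D.
4. It then claims power for the two doses, meaning the two in the trial.
5. Otherwise, 8 mg appears in this section only as the dose in the external study, which is a ready source for the slip.

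**Reproducing the plan's figure with D = 1.5 h for 1 mg versus 4 mg**

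Inputs from the plan: margin 4 h; D = 1.5 h; type 1 error 0.05/3 = 0.0167 (printed as 0.1667), taken per side; power 80%; drop-out 10%. The SD is not stated. The value tried is the half-width of the quoted interval, (27.4 − 19.5)/2 = 3.95 h.

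Sample size per arm (normal approximation):

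n = 2 × SD² × (z₁₋α + z₀.₈₀)² / (4 − 1.5)²
= 2 × 3.95² × (2.128 + 0.842)² / 2.5²
= 44.03, so 45 evaluable.

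Recruited: 45 / 0.9 = 50 per arm, the plan's figure.

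Power at 45 per arm:

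- SE = 3.95 × √(2/45) = 0.833 h
- Power = Φ((4 − 1.5)/SE − 2.128) + Φ((4 + 1.5)/SE − 2.128) − 1 = 0.809

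This agrees with the stated power above 80%. A t-based calculation gives 79.8%, which differs only through the approximation.

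**Second check, on the placebo comparison**

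The same SD should also support the plan's claim of more than 90% power for a 5 h difference with 15 placebo subjects.

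- Evaluable: 15 × 0.9 = 13.5 placebo against 45
- SE = 3.95 × √(1/13.5 + 1/45) = 1.226 h
- Power at two-sided 0.05/3 = Φ(5/1.226 − 2.394) = 0.954

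This too is consistent with the plan.

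**Effect of correcting the label**

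D = 1.5 h is already the number in the formula. Replacing 4 mg versus 8 mg by 1 mg versus 4 mg leaves n at 45 evaluable, 50 recruited, and power at 80.9%. The change is zero.

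**The case for a change.** The best argument for a correction is that power depends heavily on D, so a reader should not have to infer it. That sensitivity is real. At SD 3.95 h and 45 per arm, the power formula above gives 99.3% at D = 0, 80.9% at 1.5 h and 17.7% at 3 h (the last purely illustrative). The literal reading is also not absurd: the only duration data quoted are for 8 mg, and the authors might have meant an unstated bridge from 8 mg to 4 mg.

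Two parts of this stand. The sentence as printed is wrong or incomplete, and the documents cannot prove what was intended. The numerical match also depends on an SD that the plan does not give, and other pairs of D and SD would yield 45. The match is persuasive because both numbers come from the same section and together return exactly 50, and because the same SD fits the placebo claim.

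What does not stand is that the label puts the power in doubt. The larger uncertainty is the SD. A CI half-width is not an SD; converting it with n = 25 gives 3.95/2.064 × 5 = 9.57 h or 3.95/1.96 × 5 = 10.08 h, and t-based power at D = 1.5 h is then under 1%. That holds whichever doses are named in the sentence. The unstated SD and the misprinted 0.05/3 are separate questions, and relabelling would settle neither.

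**Conclusion.** No change is needed. The dose label is a clerical slip in one sentence of the sample size justification. The arms, the hypothesis, the margin, the null hypothesis and the list of comparisons consistently concern placebo, 1 mg and 4 mg. The planning difference plays no part in the analysis, which tests the observed difference against ±4 h. Correcting the label would move the sample size by 0 and the power by 0 percentage points.

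This rests on reading 1.5 h as the 1 mg versus 4 mg difference, which the neighbouring sentences require. The arithmetic supports it under an assumed SD of 3.95 h and a type 1 error of 0.0167 per side. If the sponsor had in fact used another difference for 1 mg versus 4 mg, the power statement would need to be revisited, but nothing in the documents suggests that. The conclusion covers the label only and does not endorse the SD behind the stated power.
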